### 8.1.4 Procedures for Handling Missing, Unused, and Spurious Data

Every effort must be made to avoid missing data. For all time-to-event endpoints, patients who do not have the event of interest will be censored at the date at which they were last known to be event-free. Missing data for quantitative endpoints will be replaced by the patient's last available value. Additional approaches for sensitivity analyses of the effects of missing data for secondary endpoints may be provided in the SAP.

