## Facilities Enrolling

**Participants:**

Weill Cornell Medical College-NewYork Presbyterian Hospital (WCMC/NYPH), Brooklyn Methodist Hospital (BMH), and NewYork-Presbyterian Queens (NYPQ)

Participant Duration:	Time it will take for each individual participant to complete all participant visits in the induction phase is 8 months. Patients who complete all 32 cycles of treatment for the entire study, if have not progressed or started new treatment, will be followed with disease evaluations every 90 days (+/- 30 days) until confirmed disease progression or for total duration of 24 months from last EOT visit, whichever comes first, and for survival for up to 10 years from date of enrollment or until death.
Study Agent/Device Name	
Intervention Description:	
Induction Phase (Cycles 1-8, q28 day cycles):
 
 
• Daratumumab 1800 mg SC weekly x 8 wks, 1800 mg SC q2wk days 1 and 15 (cycles 3-6) 1800 mg SC q4wk day 1 (cycles 7-8)
 
• Clarithromycin 500mg PO bid continuous until VGPR or 8 cycles, whichever occurs first
 
• Pomalidomide 4 mg PO days 1-21
 
• Dexamethasone 20 mg IV as premed days 1 and 8 (cycle 1); 20 mg PO days 2 and 9 (cycle 1); 40 mg PO as premed days 15 and 22 (cycle 1); 40 mg PO qwk (cycles 2-6); 20 mg PO qwk (cycles 7-8)
 
 
Maintenance Phase (Cycle 9+): up to 24 months q28 day cycles
 
 
• Daratumumab 1800 mg SC day 1
 
• Pomalidomide 4 mg PO days 1-21
 
• Dexamethasone 20 mg PO qwk
 

Primary Objective:	PRIMARY: To determine best response rate within 8 cycles of induction therapy.
Secondary Objectives:	SECONDARY: To determine median PFS and OS, time to response (TTR), time to progression (TTP), response duration, time to next therapy (TTNT), time to $\geq$ VGPR, ORR, CR or better rate, MRD negativity rate after 8 and 32 months, AEs in induction and maintenance phases, clinical response in high-risk groups.
Exploratory Objectives:	Assessment of MRD by multiparameter flow cytometry (MFC), FISH, NGS, PET/MRI imaging studies at best response. MFC-based tests of BM aspirates of both CD138-isolated clonal plasma cells and immune cells from marrow and tissue will be studied for various immune-based and daratumumab-based markers; dose-intensity analyses (mean relative dose intensity of dexamethasone); QoL assessments.
Endpoints:	Primary Endpoint:

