## **3. STUDY ENDPOINTS**

### **3.1 Primary Endpoints**

- $\geq$  VGPR response proportion as best response within 8 cycles of induction treatment

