3.3.4 Imaging (PET/MRI) at diagnosis and at best response/MRD

3.3.5 Dose intensity analysis (mean relative dose intensity of dexamethasone)

## 4. STUDY DESIGN

### 4.1 Overview of Study Design

This is a single center, single-arm phase 2 study that will be conducted at Weill Cornell Medical College to evaluate the best response within 8 cycles of induction in relapsed/refractory multiple myeloma compared to historical pomalidomide/dexamethasone. Patients will receive daratumumab/clarithromycin/ pomalidomide/dexamethasone (D-ClaPd) for 8 cycles of induction followed by daratumumab/pomalidomide/dexamethasone for maintenance until PD or unacceptable toxicity, whichever comes first. Patients will be treated for up to 24 months of maintenance if evidence of PR or better after induction.

D-ClaPd has potential for synergistic activity with good tolerability/safety in relapsed/refractory myeloma.

In patients with previous daratumumab exposure, the following hypotheses will be tested:

- D-ClaPd will yield higher  $\geq$ VGPR rates in relapsed/refractory myeloma than historical pomalidomide/dexamethasone ( $\geq$ VGPR 9%) in this setting.
- Daratumumab retreatment in combination with ClaPd in early relapse will have higher ORR than ClaPd (ORR 60%).

Patient participation will include a screening phase and a treatment phase. The screening phase will be up to 28 days prior to first dose of study drug. The Treatment Phase begins on the date of the first study treatment and ends on the date the patient and the investigator agree that the patient will no longer continue study treatment.

During the treatment phase, daratumumab, clarithromycin, pomalidomide, and dexamethasone will be administered as per the following schedule.

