#### 8.1.1 Determination of Sample Size

The sample size computations were performed assuming a 5% level of significance and 80% power. The new regimen will be declared effective and worthy of further testing if 8 or more patients have  $\geq$  VGPR among the 40 patients entered into the cohort.

Sample size recommendations for the current design are determined according to A'Hern's exact single-stage phase II design (A'Hern, RP, 2001). We project a  $\geq$  VGPR response proportion of 9%, below which the regimen will be unacceptable, and a  $\geq$  VGPR response proportion of 25%, above which the regimen will be considered worthy of further exploration. The null hypothesis that the  $\geq$  VGPR response proportion is less than or equal to 9% will be tested against the alternative hypothesis that the  $\geq$  VGPR response proportion is greater than or equal to 25%.

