##### Response

Parameters assessed will include stringent complete response (sCR), complete response (CR), very good partial response (VGPR), partial response (PR), and stable disease (SD) per standard IMWG response criteria. In addition, overall response rate (defined as greater than or equal to PR across all cycles of treatment), response duration, time-to-response (TTR), MRD negativity rate and improvement in response during maintenance therapy will be assessed.

Best overall response categories will be tabulated and overall for CR, VGPR, PR, SD, progressive disease, and relapse. A two-sided 95% exact binominal CI will be calculated for each category. The response rate (responses  $\geq$  PR) will also be tabulated. Time-to-event analyses will be done using Kaplan- Meier analyses and will include time to response, duration of response, PFS, and OS, as data allow. If there is not enough data to apply the Kaplan-Meier test, the data will be summarized by descriptive statistics.

Time to response (for responders only) will be calculated as the time from the date of first study treatment dosing to the first date of documented response (PR or better) and will be summarized by descriptive statistics.

Duration of response (for responders only) is defined as the time from the earliest date of documented response (PR or better) to the earliest date when disease progression was confirmed. Patients who are non-responders will be excluded from this analysis. Detailed censoring rules for duration of response will be specified in the SAP.

PFS will be calculated as the time from the initial administration of Daratumumab, Clarithromycin, Pomalidomide, and Dexamethasone until documented disease progression, as determined using standard response criteria, or death from any cause, whichever occurs first. Kaplan-Meier methods will be used to estimate PFS over time and the median duration of PFS. Patients with no PFS event will be censored at the date of their last disease assessment.

Time to next therapy is defined as the time from the initial administration of Daratumumab, Clarithromycin, Pomalidomide, and Dexamethasone on trial to next treatment.

OS is defined as the time from the initial administration of Daratumumab, Clarithromycin Pomalidomide and Dexamethasone to death from any cause. Kaplan-Meier methods will be used to estimate the OS function. Patients who do not die will be censored at the date that the patient was last known to be alive.

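### The last-value rule in Section 8.1.4 fills exploratory and descriptive quantitative measures with values nobody observed, and should be deleted

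*Combined protocol and SAP*

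**What the plan says.** Section 8.1.4 gives three instructions on missing data.

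- Where the outcome is a time to an event, the rule is censoring: "patients who do not have the event of interest will be censored at the date at which they were last known to be event-free".
- For the rest, "Missing data for quantitative endpoints will be replaced by the patient's last available value".
- As a supplement, "Additional approaches for sensitivity analyses of the effects of missing data for secondary endpoints may be provided in the SAP".

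The section does not define which endpoints are quantitative. It does not say whether the replacement continues after a patient stops treatment, progresses or dies. The supplement is optional and does not extend to exploratory measures.

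The primary endpoint (Section 3.1) is "VGPR response proportion as best response within 8 cycles of induction treatment", counted at VGPR or better. Section 8.1.6 assigns "very good partial response (VGPR), partial response (PR), and stable disease (SD) per standard IMWG response criteria". The secondary endpoints in Section 3.2 are proportions or times to an event.

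The quantitative measures lie elsewhere. The exploratory objectives in the Protocol Summary include "dose-intensity analyses (mean relative dose intensity of dexamethasone); QoL assessments". Item 3.3.5 repeats the first of these: "Dose intensity analysis (mean relative dose intensity of dexamethasone". Item 3.3.3 adds marrow immune-cell and daratumumab-related markers. Section 8.1.5 summarises laboratory and vital-sign values descriptively.

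**The concern.** Carrying the last value forward treats a guess as an observation. Patients leave treatment for reasons tied to their condition: Section 4.3 lists progression, unacceptable adverse events and adverse-event delays beyond 4 weeks. A value recorded before such an exit need not resemble what would have been seen afterwards. The filled value also enters means and intervals as if it had been measured, so precision is overstated.

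The marker data raise a more specific problem. Footnote o of the Schedule of Study Procedures makes the best-response marrow sample conditional on VGPR or better. Patients below VGPR have no such sample by design, so a literal reading of the rule would enter their screening result as follow-up.

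At stake is the credibility of the quality-of-life, marker, laboratory and dose-intensity summaries. The decision on whether the regimen is worth pursuing is not.

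**Working it through.** **1. The plan's own design figure.** Section 8.1.1 says "The sample size computations were performed assuming a 5% level of significance and 80% power", with 40 patients, success at 8 or more, a null rate of 9% and a target of 25%. With X the number at VGPR or better:

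- P(X ≥ 8 | n = 40, p = 0.09) = 0.0242
- P(X ≥ 8 | n = 40, p = 0.25) = 0.818

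Both stated bounds are met, and neither figure involves carry-forward.

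**2. Does the rule change best response?** Let a patient's assessed categories be x1, …, xd, with nothing after assessment d. Carrying forward adds copies of xd, and max(x1, …, xd, xd, …) = max(x1, …, xd). Best response is the same. A check on 200,000 randomly generated eight-cycle paths with random dropout gave 0 changes.

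**3. Marrow markers.** Assumptions: all 40 patients have a screening value, and an untaken best-response sample is treated as missing. Patients below VGPR then contribute a change of exactly zero. If m patients are sampled at best response and their mean change is D, the mean change over 40 after filling is (m × D)/40.

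| Share at VGPR or better | Sampled, m | Filled with screening value | Mean change after filling |
|---|---|---|---|
| 25% (target) | 10 | 30 | 0.25 D |
| 20% (8 of 40, success boundary) | 8 | 32 | 0.20 D |
| 9% (null) | 3.6 expected | 36.4 expected | 0.09 D |

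**4. Dexamethasone dose intensity.** Planned doses come from Section 6.2.4 (patients under 70). Cycle 1 is 4 × 20 + 2 × 40 = 160 mg. Cycles 2–6 are 4 × 40 = 160 mg each. Cycles 7–8 are 4 × 20 = 80 mg each. The total is 6 × 160 + 2 × 80 = 1120 mg. The induction schedule for patients of 70 or over is half of this throughout, so the ratios are the same.

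Assumptions, since the plan defines neither numerator nor denominator: the denominator is the full eight-cycle plan, patients take full dose until they stop, and doses after stopping are treated as missing and filled with the last cycle's amount.

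| Stops after cycle | From recorded doses | With carry-forward |
|---|---|---|
| 2 | 320/1120 = 29% | (320 + 6 × 160)/1120 = 114% |
| 4 | 640/1120 = 57% | (640 + 4 × 160)/1120 = 114% |
| 6 | 960/1120 = 86% | (960 + 2 × 160)/1120 = 114% |

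The filled figure is 114% whenever the patient stops, because the planned reduction at cycle 7 is never applied.

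The documents give no dropout figure. If a share f stops after cycle 4 and the others take full dose, the mean is (1 − f) + f × 0.571 from recorded doses and (1 − f) + f × 1.143 with carry-forward.

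| f (assumed) | Recorded doses | Carry-forward | Difference |
|---|---|---|---|
| 10% | 95.7% | 101.4% | 5.7 points |
| 20% | 91.4% | 102.9% | 11.4 points |
| 30% | 87.1% | 104.3% | 17.1 points |

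Reported intensity rises as more patients stop. If filled intensity were capped at 100% of plan, the differences would be 4.3, 8.6 and 12.9 points. If the denominator ended at the stopping date, or later doses counted as zero, carry-forward would have no effect.

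**5. Quality of life and laboratory values.** No size can be given. The documents state no dropout, no quality-of-life instrument and no quality-of-life row in the Schedule of Study Procedures.

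**The case against.** A reader might infer something stronger: that carrying M-protein forward could confirm a VGPR that was never re-measured, and so inflate the primary result. The arithmetic is easy to produce. With one patient certain to be falsely confirmed and the other 39 at 9%, P(X ≥ 7 | n = 39) = 0.0570, against 0.0242. The documents do not support this reading. M-protein and light chains are assessments, not listed endpoints. No confirmation rule is spelled out, and nothing says an imputed value may serve as an assessment. The 0.0570 is also conditional on a false confirmation that no passage makes likely, so it is not the trial's error rate.

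The other objections are partly right.

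- **Dose intensity.** A dose not taken after stopping is ordinarily zero or outside the denominator, not missing. That stands, so the figures above are conditional. The plan's silence on both definitions is what leaves the reading open.
- **Direction.** A patient who stops for acute toxicity may have a last laboratory value worse than the later one. That stands: outside dose intensity and the marker dilution, the bias could go either way.
- **Remedy.** A repeated-measures model suits sparse, response-conditional marker samples poorly. That stands, and the fix allows for it.
- **Harmlessness.** That the affected measures are exploratory limits the importance. It does not justify a rule that makes them less accurate when followed.

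**Conclusion.** The point holds for exploratory and descriptive quantitative measures only. Section 8.1.4 prescribes single-value carry-forward without limit and without a required sensitivity analysis. Following it would create values that were not observed, attach no uncertainty to them, and could bias the summaries.

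The clearest case is the markers. At the target rate, 30 of 40 best-response values would be screening values and the mean change would shrink to a quarter of that in sampled patients, provided untaken samples are treated as missing. Mean dose intensity could be overstated by about 6 to 17 points if 10% to 30% of patients stop after cycle 4. That rests on the assumed dropout, the full eight-cycle denominator and post-stopping doses being treated as missing.

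The primary best-response test is not altered as written. Time-to-event endpoints are also outside the rule, because the same section censors them.

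**What to change.** Delete the carry-forward sentence from Section 8.1.4 and replace it with the following.

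1. Quantitative measures are analysed as observed, with the number of patients contributing at each time point.
2. A likelihood-based repeated-measures model is used only where there are enough scheduled repeats. Quality of life would qualify once an instrument and schedule are stated.
3. Marrow markers are summarised as paired observed values (screening and best response) in patients who have both, described as conditional on VGPR or better.
4. Dexamethasone dose intensity is computed from recorded doses only, with the denominator stated.
5. Disease assessments are never imputed, and an imputed value cannot establish or confirm a response. This closes off the stronger reading at no cost.

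The sample size and the rule of 8 in 40 stay as they are. The cost is a wording change, fewer patients in some exploratory summaries, and slightly less favourable figures where carry-forward would have flattered them.

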### 8.1.5 Safety Analysis

Safety parameters will include SAEs, TEAEs, physical examination findings (including ECOG performance status), vital sign measurements, standard clinical laboratory parameters (serum chemistry, hematology, urinalysis), and ECG parameters. Adverse events will be graded according to the NCI-CTCAE v4. The incidence of DLTs will also be evaluated.

Safety analyses in general will be descriptive and will be presented in tabular format with the appropriate summary statistics.

A TEAE is defined as an adverse event that emerges during the treatment period (from first dose date till 30 ( $\pm$  5) days after the last dosing date), having been absent at pre-treatment; or reemerges during treatment, having been present at baseline but stopped prior to treatment; or worsens in severity after starting treatment relative to the pre-treatment state, when the adverse event is continuous. The number and percentage of patients reporting TEAEs will be tabulated by the worst NCI-CTCAE grade, system organ class (SOC), and preferred term.

Similarly, the number and percentage of patients reporting treatment-emergent SAEs will be tabulated, as well as TEAEs/SAEs considered related to Daratumumab, Clarithromycin, Pomalidomide, and Dexamethasone.

A by-patient AE (including TEAE) data listing will be provided including, but not limited to, verbatim term, preferred term, SOC, NCI-CTCAE grade, and relationship to study drug.

Deaths, other SAEs, and other significant adverse events, including those leading to permanent discontinuation from Daratumumab, Pomalidomide, and Dexamethasone, will be listed.

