### SCHEDULE OF STUDY PROCEDURES

Screening Phase  Day-28 to 0		Treatment	End of Treatm	Post-Treatment Observation Phase
		(Cycle is 28 days) +/- 3 days for Cycle 1 and 2, +/- 7 days for Cycles 3-30	At 1 year (+/- 7 days) & 90 days after last dose of study drug (+/-7 days)	Each cycle is 90 days, +/- 30 days for 24 months or until progression
Informed consent a	X			
Inclusion/exclusion criteria review	X			
Demography/Medical history	X			
Physical Exam	X	X b (every cycle)	X	
Vital signs c	X	X d (every cycle)	X	
Weight	X	X (every cycle)	X	
ECOG status	X	X (every cycle)	X	
ECG	X			
Echocardiogram	X		X	
Pulmonary function testing e	X e		X e	
Chest x-ray f				
NYHA classification	X	X (cycle 1 only)	X	
Patient Diary g	X	X (every cycle)	X	
Concomitant medications	Continuous from time of ICF until 30 days of last treatment			
Adverse events	Continuous from time of ICF until 30 days of last treatment			
Study Drug Administration				
Daratumumab 1800 mg SC dosing h		Daratumumab 1800 mg SC on Days 1, 8, 15, and 22 of Cycles 1 and 2 (weekly dosing), on Days 1 and 15 of Cycles 3 to 6 (every 2 weeks dosing), and on Day 1 of Cycle 7 and subsequent cycles (every 4 weeks dosing)		

Clarithromycin		500 mg PO bid continuous days 1-28 of cycles 1-8 only		
Pomalidomide		Pomalidomide 4 mg PO days 1-21		

Dexamethasone		Dexamethasone (Cycle 1 D1 & 8): 20 mg IV Cycle 1 D2 & D9: 20mg PO Cycle 1 D15 & D22: 40mg PO Cycles 2- 6: 40 mg PO qwk Cycles 7- 8: 20mg PO qwk Cycle 9+: 20mg PO qwk		
Prophylactic Medications				
Varicella Zoster Prophylaxis		Valacyclovir 500mg PO qd (or equivalent, renally dosed-adjusted)		
Gastrointestinal Prophylaxis		Pantoprazole 40 mg PO daily, or other		
Laboratory Assessments				
Pregnancy test i	X	X	X	
Blood typing/indirect antiglobulin test	X			
Hematology (CBC) with differential	X	On Days 1, 8, 15, and 22 for Cycles 1 and 2; On Days 1 and 15 for Cycles 3 through 6; D1 from Cycle 7 onward and as clinically indicated	X	
Serum chemistry j	X	On Days 1, 8, 15, and 22 for Cycle 1-2, Day 1, 15 for cycles 3-6 and day 1 of each subsequent cycle	X	
Hepatitis B and C screening k	X	HBV DNA monitoring q12weeks	X	X i
Disease Assessments				
Serum $\beta$ 2-microglobulin	X			
Serum free light chains	X	X (every cycle)	X	X (every cycle)

SPEP and IFE	X	X (every cycle)	X	X (every cycle)

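### Adverse events by phase are a stated secondary objective, but no planned safety table separates induction from maintenance

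*Combined protocol and SAP*

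**What the plan says.** **Objective.** The Secondary Objectives row of the Protocol Summary includes "AEs in induction and maintenance phases, clinical response in high-risk groups". Section 2.2 (Secondary Objectives) and Section 3.2 (Secondary Endpoints) list no adverse-event item.

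**Planned analysis.** Section 8.1.5 sets a single window: "A TEAE is defined as an adverse event that emerges during the treatment period (from first dose date till 30" (±5) days after the last dose. Within it, "The number and percentage of patients reporting TEAEs will be tabulated by the worst NCI-CTCAE grade, system organ class (SOC), and preferred term". Treatment-emergent SAEs are tabulated in the same way, "as well as TEAEs/SAEs considered related to Daratumumab, Clarithromycin, Pomalidomide, and Dexamethasone". There is also a listing: "A by-patient AE (including TEAE) data listing will be provided including, but not limited to, verbatim term, preferred term, SOC, NCI-CTCAE grade", with relationship to study drug. None of these is divided by phase. Section 8.1.3 defines an enrolled set and a full analysis set, but no safety set and no maintenance set.

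**Who enters maintenance.** Section 4.1: "Patients will be treated for up to 24 months of maintenance if evidence of PR or better after induction".

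**Clarithromycin.** The Summary gives "Clarithromycin 500mg PO bid continuous until VGPR or 8 cycles, whichever occurs first", and the Section 4.1 cycle schedules also stop it at VGPR. The Schedule of Study Procedures gives "500 mg PO bid continuous days 1-28 of cycles 1-8 only", with no stop at VGPR.

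**The concern.** A secondary objective that names two phases needs an analysis that distinguishes them. Section 8.1.6 does this for efficacy, where improvement in response during maintenance is assessed. Section 8.1.5 has no safety counterpart.

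The phases differ in drugs given and in patients at risk. The protocol also gives a reason to expect different toxicity: Section 1.1 says clarithromycin slows dexamethasone clearance and so raises steroid exposure, and the drug is given only in induction.

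A single-window, worst-grade table loses the maintenance picture in two ways:

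- **Denominator.** Maintenance events are related to all treated patients, including those who never started maintenance.
- **Masking.** A patient counted once per term at worst grade in induction adds nothing for a later event of the same term at the same or a lower grade.

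At stake is whether the report can say how tolerable the long maintenance phase was for those who received it.

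**Working it through.** The plan gives no figure for phase-specific safety. Its one design figure, success at 8 or more of 40, reproduces by exact binomial: type I error 0.024 at 9% and power 0.818 at 25%. Nothing below changes it.

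**Inputs**

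- Treated patients: 40 (Section 4.2).
- Entry to maintenance: PR or better after induction (Section 4.1). The protocol does not project how many this will be, so reference ORRs from Section 1.1 serve as a proxy. The low end is 12.5%, for daratumumab-pomalidomide-dexamethasone in patients refractory to both daratumumab and pomalidomide. The high end is 60%, for ClaPd.
- Grade 3-4 neutropenia: 77% on daratumumab-pomalidomide-dexamethasone (Section 1.3.2.2). It is used here as an assumed induction rate, although the source figure covers that study's treatment generally.
- Maintenance event rates: assumed, for illustration.

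**Step 1: entrants, m = 40 × ORR**

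40 × 0.125 = 5, and 40 × 0.60 = 24. ORR counts a response at any time, so progression or withdrawal before cycle 9 would lower m.

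**Step 2: dilution**

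If x patients have a first event in maintenance, the phase rate is x/m and the contribution to a pooled table is x/40. With x = 5 and m = 24:

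| Denominator | Rate | Exact 95% CI |
|---|---|---|
| Entrants, 5/24 | 20.8% | 7.1% to 42.2% |
| All treated, 5/40 | 12.5% | 4.2% to 26.8% |

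In general the pooled contribution is the phase rate times m/40. A 20% maintenance rate contributes 0.20 × 24/40 = 12% with 24 entrants, and 0.20 × 5/40 = 2.5% with 5.

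**Step 3: masking**

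Let p be the induction rate and q the maintenance rate. Assume that events in the two phases are independent and that entrants share the induction rate. Then the pooled ever-rate is p + (m/40) × q × (1 − p). With p = 0.77 and q = 0.40:

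| m | Calculation | Pooled rate | Visible increase |
|---|---|---|---|
| 24 | 0.77 + 0.60 × 0.40 × 0.23 | 82.5% | 5.5 points |
| 16 | 0.77 + 0.40 × 0.40 × 0.23 | 80.7% | 3.7 points |
| 5 | 0.77 + 0.125 × 0.40 × 0.23 | 78.15% | 1.15 points |

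A 40% rate among those in maintenance would thus appear as a rise of about 1 to 6 points.

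**Step 4: phase boundaries**

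The end of induction is stable at cycle 8, but the length of maintenance is not. Section 4.1 heads the maintenance schedule cycles 9-30 and Section 4.3 allows up to 30. The Summary and Section 7.4 refer to 32 cycles. Section 6.11 says up to 12. Exposure-adjusted rates need one definition.

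**The case against.** **The plan does not forbid a phase split.** Pooling is inferred from the single window and the absence of any split. Section 8.1.5 promises descriptive tables in general terms, and its listing is open-ended, so by-phase tables could be produced afterwards. This stands as far as it goes: the plan under-specifies and does not prohibit. But an analysis for a named secondary objective should be specified in advance.

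**The objective appears once.** Section 1.1 names only toxicity of the combination, which an overall table addresses. That is a reason to align the sections; it does not remove the objective from the Summary.

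**Five of 40 is a legitimate figure.** It is a cumulative incidence among treated patients. True, but it does not describe toxicity in patients receiving maintenance.

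**Stronger readings that the documents do not support:**

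- A reader might infer that the worst-grade table is the only one planned. Tables of serious and related events are planned too; they are simply not split.
- A reader might infer that clarithromycin harm could not be seen at all, or that a phase split would isolate it. The related-event summaries name clarithromycin, so investigator-attributed events can appear. By the Summary and Section 4.1 the drug may stop at VGPR within induction, so induction can mix time on and off it. Patients entering maintenance are also selected by response. A phase contrast is therefore not a clarithromycin contrast.
- A reader might take the median PFS values in Section 1.1 (7.7 and 8.8 months) to conclude that 21 to 22 patients reach cycle 9. Those medians come from other studies, the second discussed under daratumumab-naïve disease, and the calculation ignores the PR requirement. The precision would be false.

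**Conclusion.** The point holds as a mismatch between objective and analysis: the Summary asks for adverse events by phase, and no table in Section 8.1.5 supplies them. The direction of dilution follows whenever fewer than 40 patients enter maintenance; masking follows from counting each patient once per term at worst grade.

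The size depends on assumptions. Entry of 5 to 24 patients rests on reference response rates from other populations, and the event counts and rates are illustrative. The masking figures also assume independence between phases. Section 8.1.5 names no denominator, so all 40 treated patients is itself an inference.

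No decision rule in the plan uses a phase comparison, and neither sample size nor the primary analysis is affected. By-phase rates will be imprecise, as the interval for 5 of 24 shows, and should be read descriptively.

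**What to change.** 1. In Section 8.1.5, tabulate TEAEs, SAEs and related events separately for induction (cycles 1-8) and maintenance (cycle 9 onward). Assign events by onset date. Count an event that worsens after cycle 9 day 1 in maintenance at its new grade, in line with the existing TEAE definition.
2. Use patients who started each phase as the denominator, with worst grade taken within phase. Add exposure-adjusted rates, such as patients with an event per 100 patient-cycles. Keep the pooled table as a supplement.
3. Define a safety set and a maintenance set in Section 8.1.3.
4. Add the objective to Sections 2.2 and 3.2 so that they match the Summary.
5. If clarithromycin toxicity is of interest, add a descriptive summary of events on versus off the drug. Otherwise make no claim about it from the phase tables.
6. Reconcile the statements on when clarithromycin stops (Summary, Schedule of Study Procedures, Section 4.1) and on total cycles (Summary, Sections 4.1, 4.3, 6.11 and 7.4), so that the phase windows are defined.

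The cost is wording and additional table shells, with no extra patients or visits. The Schedule already has adverse events recorded continuously, and the TEAE definition requires their timing. Onset date is not among the listing fields named in Section 8.1.5, so onset date and phase should be added there and the case report form checked for them.
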